6.5 Administration of study drug

Prior to first drug administration, patients will be counselled on how to take BAL101553. A drug diary will be provided to the patient to record their daily drug intake and will include:

- The cycle number and week number.
- The number, frequency and dosing-strength of capsules to be taken each day.
- The contact information of the Principal Investigator.
- The date of study drug intake (to be filled in by the patient each day).
- Confirmation that study drug was taken as instructed (to be filled in by the patient each day).
- An area for comments.

Patients must have observed the fasting period described in Section 3.1.4. Capsules must be taken with (at least) 250 mL of still water. No other intake of food is permitted for 1 h after taking the dose. Instructions on what to do in the case of a missed dose are presented in Section 3.2.7.

6.6 Compliance and drug supply accountability

6.6.1 Compliance

The Investigator or designee is responsible for drug accountability, reconciliation and record maintenance for used and unused study drug. The drug accountability records must be kept current and must be available for monitoring by the clinical research associate (CRA). The logs and all other forms or documents relating to overall drug accountability must be collected from study center by the CRA.

Further details on drug accountability will be provided to the study centers prior to study initiation.

Study drug must not be used for any purpose other than the study.

Study drug must not be used after the retest date unless its release date has been extended based on updated information from ongoing stability studies.

All oral dosing on PK sampling days must take place in the clinical study unit. Compliance will be assessed by review of patient drug diaries and returned capsule counts.

6.6.2 Drug supply

A Drug Dispensing Log must be kept current and must contain the following information:

- Shipments received
- Date(s), quantity and batch number of the drug dispensed to the patient
- Identification of the patient to whom the drug was dispensed
- Date(s), quantity and batch number of the drug returned to the site
- Principal Investigator name
- Quantity of the drug remaining

The inventory must be available for inspection by the Sponsor's CRA(s). All supplies, including partially filled or empty bottles and the dispensing logs, must be kept at the pharmacy to be checked by the Sponsor's CRA(s) either after each dose cohort or at the end of the study.

6.6.3 Drug disposal

After performance of drug accountability and review by the CRA, partially used or empty bottles of study drug may be destroyed at the study center according to standard institutional procedures. The Investigator (or designee) must maintain records of any such destruction. These records must show the identification and quantity of each unit disposed of, the method of destruction (taking into account the requirements of local law), and the person who disposed of the study drug.

If study drug cannot be destroyed at the study center, off-site destruction will be organized by the CRA.

7 PATIENT SAFETY

7.1 Adverse events

7.1.1 Definition of adverse events

An AE is any adverse change from the patient's baseline (pre-therapy) medical condition which occurs during the course of a clinical study, from the start of first study medication, whether considered related to treatment or not.

An event involving the exacerbation or worsening of a pre-existing illnesses must be recorded as an AE. However, lack of efficacy or insufficient clinical response should not be recorded as an AE.

In this study, a treatment-emergent AE is defined as any AE occurring between first administration of study drug and last scheduled follow-up contact (28 days after last study administration).

Abnormal laboratory values or test results constitute AEs only if they induce clinical signs or symptoms, are considered clinically significant, or require therapy. These test results must be recorded on the AEs page of the CRF, under the signs, symptoms or diagnosis associated with them.

7.1.2 Evaluation of adverse events

The severity of AEs will be assessed according to the National Cancer Institute Common Terminology Criteria for Adverse Events version 4.03 (CTCAE) (Phase 1) and v5.0 (Phase 2a).

Details of the CTCAE can be found here:

https://ctep.cancer.gov/protocolDevelopment/electronic_applications/ctc.htm

For AEs that can be described by the CTCAE 5.0 guidelines, the CTCAE Grade 4 (life-threatening or disabling AE) is assessed based on unique clinical descriptions of severity for each AE, and these criteria may be different from those used for the assessment of AE seriousness. An AE assessed as Grade 4 based on the CTCAE grades may or may not be assessed as serious based on the seriousness criteria.

The relationship of AEs to the study treatment will be assessed as:

- Not related
- Unlikely
- Possible
- Probable

Appendix 7 provides criteria for relationship assessments.

7.1.3 Documentation of adverse events

All AEs occurring after the start of first study drug administration must be reported on the AE CRF pages.

Serious adverse events (SAEs) must be reported from the time of informed consent to allow for an assessment of serious procedure related events, i.e., serious events/complications related to the screening study procedures (see Section 7.2).

Non-serious AEs that occur between informed consent and first study drug administration will be collected as pre-dose medical history.

If possible, a diagnosis should be documented rather than signs and symptoms. All AEs must be recorded in English language. Each AE should be described by:

- 1. Its duration (start and end dates).
- 2. The severity grade (CTCAE grade 1–4, or 3-point scale, see Section 7.1.2).
- 3. Its relationship to the study treatment (assessment of causality, see Section 7.1.2 and Appendix 7).
- 4. The action(s) taken with regards to the study treatment or additional treatments given for the event.
- 5. Whether it is an SAE (see Section 7.2).
- 6. The outcome.

7.1.4 Progression of the disease under study

Progression of disease is considered an efficacy outcome parameter and should not be captured as an AE or SAE, unless its outcome is death. However, symptoms of disease progression should be recorded as AEs. If the symptoms of disease progression meet the seriousness criteria, the AE will be reportable to the Sponsor as an SAE (see Section 7.2).

7.2 Serious adverse events

Any SAE occurring from informed consent signature until last scheduled follow-up contact, irrespective of the treatment received by the patient, must be reported to the Sponsor or designated safety representative within one working day of awareness of the event (see below).

7.2.1 Definition of serious adverse events

An SAE is any AE that at any dose that:

- Results in death.
- Is life-threatening.
- Requires inpatient hospitalization or prolongation of existing hospitalization;
- Results in persistent or significant disability/incapacity.
- Is a congenital anomaly/birth defect.

Medical and scientific judgment should be exercised in deciding whether expedited reporting to the Sponsor is appropriate in other situations, such as important medical events that may not be immediately life-threatening or result in death or hospitalization but may jeopardize the patient or may require intervention to prevent one of the outcomes listed in the definitions above. These situations should also usually be considered serious.

Examples of such events are intensive treatment in an emergency room or at home for allergic bronchospasm; blood dyscrasias or convulsions that do not result in hospitalization; or development of drug dependency or drug abuse.

Note: Death is considered an outcome of an AE. Whenever possible the underlying cause of death must be reported as the AE.

A life-threatening AE is any adverse experience that places the patient at risk of death from the reaction at the time it occurred, i.e., it does not include a reaction that, had it occurred in a more severe form, might have caused death.

Inpatient hospitalization is defined as any inpatient admission (even if less than 24 h).

Preplanned hospitalizations and elective surgery, which are not due to a worsening or exacerbation of an underlying disease, would not constitute an SAE.

7.2.2 Unexpected adverse event or serious adverse event

An unexpected AE or SAE is one for which the nature or severity of the event is not consistent with the applicable Reference Safety Information (Section 6 of the Investigator's Brochure).

7.2.3 Reporting of serious adverse events

Any SAEs occurring from informed consent form signature until the last follow-up contact, whether considered treatment-related or not, must be reported immediately to the Sponsor's safety representative listed hereunder within 24 h of awareness of the event. SAEs regardless of relationship to treatment will be collected until the last scheduled follow-up contact (28 days after last study drug administration).

AE reporting will not be solicited after the last scheduled follow-up contact, however any SAEs (including deaths) that occur after this time must be reported, if considered related to study drug.

Safety contact

The Sponsor's safety representative must submit expeditable SAEs to health care authorities and the central Independent Ethics Committee/Institutional Review Boards (IEC/IRB), as required by national law. Expectedness of serious adverse drug reactions related to BAL101553 will be assessed against the applicable Investigator's Brochure.

The Investigator must notify the local IEC/IRB of an SAE in writing, in accordance with local laws and regulations.

7.2.4 Documentation of serious adverse events

The description of the AE must be as complete as possible and allow for a medical assessment of the case. As a minimum, the SAE report must at least contain:

- A subject identifier.
- An AE description, including severity of the event.
- Action taken with regards to study treatment.
- Outcome information.
- The Investigator's causality assessment.

Such preliminary reports must be followed later by detailed descriptions, which may include copies of hospital case reports, autopsy reports, and other documents if requested and applicable.

Causality must be rated by the Investigator according to Appendix 7. A causal relationship is suspected for all AEs reported with a relationship of 'possible', 'probable' and those with missing or unknown relationships.

7.2.5 Treatment and follow-up of adverse events

The Investigator or other physician in attendance must administer therapy as clinically indicated. All study-related SAEs and AEs must be followed-up until they have returned to baseline status or stabilized. If a clear explanation is established, it must be recorded on the CRF.

Any AE which remains unresolved after completion of the study requires detailed evaluation, follow-up and, if necessary, specific medical treatment until the AE is resolved or a reasonable explanation for its persistence is found.

7.2.6 Follow-up of abnormal laboratory test results

In the event of unexplained, abnormal laboratory test values, the tests must be repeated and followed-up until they have returned to the normal range (or baseline level) and/or an adequate explanation of the abnormality is found. If a clear explanation is established, it must be recorded on the CRF.

7.3 Pregnancy

Reproductive and fertility studies in animals have not been performed with BAL101553, therefore, female patients of childbearing potential must not become pregnant while being treated with BAL101553.

The Investigator must make every effort to ensure that neither a clinical trial patient, nor their partner, becomes pregnant during the trial or within the 3 months after the last dose of study drug. This should be done and documented as part of the consent process, by explaining clearly to the patient the potential dangers of becoming pregnant and also providing each patient with information about appropriate medically-approved effective contraception.

Women of childbearing potential must have negative serum pregnancy tests as described in Section 7.3, and must agree to use highly effective contraceptive methods for the duration of the study, and for an additional 90 days, as described in Inclusion criterion 7 (see Section 4.2).

Female patients must inform the Investigator within 24 hours if they have experienced a ruptured condom, or any other concerns about possible reduction of contraceptive effectivity (i.e. forgotten pill or vomiting) during the study. In these cases the patients must return to the study site as soon as possible, but not later than 24 hours, after the Investigator is informed.

Female patients must inform the Investigator if they become pregnant during the study or within the 3 months following the last study drug administration. A pregnancy must be reported by submitting a Pregnancy Report Form, according to the requirements (timelines and contact details) of an SAE (see Section 7.2.3). The patient must be monitored until conclusion of the pregnancy and infants must be followed-up at least for 8 weeks after delivery.

The Investigator must immediately notify the safety contact (see Section 7.2.3) about any pregnancy. In addition, pregnancies resulting in an adverse outcome must be reported as SAEs. Induced abortion if not for an AE would not constitute an SAE.

The Investigator must notify the local IEC/IRB about any pregnancies resulting in an adverse outcome, according to local regulations and laws.

8 STATISTICAL CONSIDERATIONS AND ANALYTICAL PLAN

PK parameters will be derived using Phoenix WinNonLin 6.3 software (Pharsight Corporation a CertaraTM Company, Saint Louis, MO, US). All analyses and data presentations will be generated using SAS® Version 9.3 or higher software (SAS Institute, Cary, North Carolina, USA).

8.1 Study variables

Primary study endpoints:

- Phase 1: Frequency and characteristics of BAL101553-related DLT, or other toxicities which are relevant for determination of the MTD.
- Phase 2a expansion portion (Simon's two-stage design): Best objective response according to RANO criteria.

Secondary endpoints:

- Overall safety endpoints:
 - Type and frequency of AE, SAEs, laboratory, echocardiogram and ECG abnormalities; abnormalities in vital signs, physical examination results, chest X-ray/CT; frequency and causes of study withdrawals and dose modifications.
- Efficacy endpoints:
 - Best objective response according to RECIST 1.1 in patients with solid tumors, based on the change from baseline in tumor measurements as measured in patients with measurable disease, and according to RANO criteria in patients with progressive or recurrent GBM or high-grade glioma (Phase 1 only).
 - Change from baseline in tumor markers (CA-125, PSA) in patients whose disease is characterized by these tumor markers utilizing Rustin criteria for ovarian cancer or PSA Working Group 2 criteria for prostate cancer.
 - Progression-free survival and OS.
- Pharmacokinetic assessments (BAL101553 and BAL27862):
 - C_{max}, T_{max}, AUC_{0-t}, AUC_{0-τ}, AUC_{0-last}, AUC_{0-∞}, t_{√2}, systemic clearance and volume of distribution.
 - Total 24 h urinary excretion of BAL101553 and BAL27862.
- Exploratory endpoints:
 - Change from baseline in biomarkers (including but not limited to numbers of CTCs, CECs, CEPs).

8.2 End of study

The end of the study is defined as the completion of the last study-related contact with any patient.

8.3 Statistical and analytical methods

8.3.1 Analysis populations

Separate analyses will be provided for patients with advanced or recurrent solid tumors and for patients with recurrent or progressive GBM or high-grade glioma in the Phase 1 dose escalation portion of the study, and for patients with recurrent GBM in the Phase 2a expansion portion (Simon's two-stage design) of the study. Separate analyses will also be performed for the Surgical cohort in the Phase 2a expansion portion of the study; this separate cohort will be performed as a single-arm study if futility is rejected in Stage 1 of the Simon's two-stage study portion, and will include patients with planned re-resection of recurrent GBM to determine brain tumor tissue levels of BAL27862. Details of analyses in this Surgical cohort will be provided in a separate protocol amendment.

8.3.1.1 Full analysis population

The full analysis population (FAP) includes all patients who received at least one partial or complete dose of study drug, based on the intent-to-treat principle. The FAP will be the primary population for analyzing efficacy in Phase 1.

8.3.1.2 Safety population

All patients who receive at least one full or partial dose of BAL101553 and had at least one post-baseline safety assessment must be included in the safety analysis population. In this context, documented information that a patient had no AEs constitutes a safety assessment. The safety analysis population must be used for all safety related analyses (AEs, vital signs, laboratory data, etc.).

For efficacy and safety analyses, patients will be primarily analyzed according to their originally assigned dose group. In the case that intra-patient dose escalation occurs in a substantial number of patients, additional analyses may be produced.

8.3.1.3 Maximum tolerated dose-determining population (Phase 1 dose escalation portion)

The MTD-determining population includes all patients from the safety set who meet the following minimum criteria during the first 28-day treatment cycle (Cycle 1):

- Received at least one dose of BAL101553 and has experienced a DLT.
- Received at least 24 of the scheduled 28 doses for q24h BAL101553 administration, or at least 48 of the scheduled 56 doses for q12h BAL101553 administration, without experiencing a DLT (including the ability to initiate treatment Cycle 2), have been observed for ≥ 28 days following the first dose and have been evaluated for safety.

Patients who do not meet these minimum evaluation requirements will be regarded as ineligible for the MTD-determining population. These patients will be included in the full analysis/safety population but will be excluded from the calculation of DLT incidence and will be replaced by recruitment of additional patients.

Patients who received less than 85% of the scheduled doses (i.e., less than 24 of the scheduled 28 doses using a once-daily regimen, or less than 48 out of the scheduled 56 doses using a twice-daily regimen) during Cycle 1, will only be considered as valid for the MDT-determining population if these patients experience a subsequent DLT during Cycle 1. Patients who have received a lower than assigned dose and have tolerated BAL101553 without a DLT will be excluded from the MTD determining population, as the toxicity assessment is not considered to be representative for the originally assigned dose level.

Patients who receive more than 125% of the assigned dose during Cycle 1 (total dose for the 28-day cycle), e.g., due to an administration error, will only be considered as valid for the MTD determining population if these patients experience no subsequent DLT during Cycle 1.

8.3.1.4 Pharmacokinetic analysis population

The PK analysis set includes all patients who received at least one dose of study drug and had at least one post-baseline pharmacokinetic assessment.

8.3.1.5 Efficacy-evaluable population (Phase 2a expansion portion of the study, Simon's two-stage design)

The efficacy evaluable population (EEP) is the subset of the FAP who had at least one postbaseline RANO assessment after having received at least 6 weeks of study treatment.

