3.1.1 Treatment cycles

Each treatment cycle will comprise 28 days of continuous, daily oral BAL101553 administration to patients in a fasted state. Section 3.2.6 describes the planned treatment duration.

Treatment may be administered on an inpatient or outpatient basis.

In the Phase 1 dose-escalation portion of the study, patients will be replaced if the minimum safety evaluation requirements for assessment of the MTD in Cycle 1 have not been met (see Sections 3.1.2 and 4.5).

In the Phase 2a dose expansion portion of the study, patients with measurable disease at baseline will be replaced if they could not complete at least one post-baseline RANO assessment after at least 6 weeks of study treatment (see Sections 3.1.3 and 4.5).

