4.5 Replacement of patients

Patients in the dose escalation portion of the study (Section 3.1.2) must meet the following minimum safety evaluation requirements in Cycle 1:

- Received at least one dose of BAL101553 and experienced a DLT.
- Received at least 24 of the scheduled 28 doses of BAL101553 for q24h administration, or at least 48 of the scheduled 56 doses of BAL101553 for q12h administration, without experiencing a DLT (including the ability to initiate treatment Cycle 2), have been observed for ≥ 28 days following the first dose, and have been evaluated for safety.

BAL101553 Clinical Study Protocol CDI-CS-002

Version 11.0 1 July 2021, page 61 of 135

The correct dose must be given as described in Section 6.5.

Patients who do not meet these minimum requirements in the dose escalation portion of the study will be replaced by recruitment of new patients.

In the Phase 2a dose expansion portion of the study (Simon's two-stage design, see Section 3.1.3), patients with measurable disease at baseline who discontinue the study treatment will be replaced if they did not have at least one postbaseline RANO assessment after having received at least 6 weeks of study treatment.

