Blood samples for PK analysis will be collected at serial time-points, as described in Section 5.7.1. 24-h urine sampling will be performed in solid-tumor patients during the Phase 1 portion of the trial for analysis of drug and drug metabolite excretion (see Section 5.7.2). Urine PK samples will not be taken from GBM/high-grade glioma patients.

Blood samples for biomarker analysis will be obtained on Day 1 of Cycle 1 as described in Section 5.8.1.

5.3.2.2 Day 8, Day 15, Day 22 and Day 28 of Cycle 1 and Cycle 2

Patients will return to the clinic and assessments will be performed in accordance with Table 8, or Table 9 for patients in the Phase 2a portion of the study. Day 28 assessments of a given cycle may be performed on Day 29 of that cycle, i.e., pre-dose on Day 1 of the subsequent cycle.

On the day of drug administration, all patients must have fasted for at least 4 h (see Section 3.1.4 for more details).

Vital signs will be performed pre-dose and post-dose as described in Section 5.5.4; ECG will be performed pre-dose and post-dose as described in Section 5.5.5.

BP measurements should be obtained pre-dose and post-dose, as described in Section 5.5.4 and Table 10.

Laboratory safety tests (hematology, biochemistry and cardiac troponin) will be assessed as described in Section 5.5.7.

Blood samples for pharmacokinetic (PK) analysis will be collected pre-dose on Day 8, Day 15 and Day 22 of Cycles 1 (both Phases) and 2 (Phase 1), as described in Section 5.7.1.

Blood samples for biomarker analysis in Phase 1 will be obtained pre-dose on Day 8, Day 15 and Day 22 of Cycle 1; and Day 22 Cycle 2; as described in Section 5.8.1.1.

In Phase 1, tumor biopsies will be obtained on Day 22 of Cycle 1 and/ Cycle 2, if easily accessible and deemed safe for the patient by the Investigator, and if the patient is willing to undergo biopsy (see Section 5.8.1.2).

Patients with measurable tumors will undergo radiological assessment of the tumor between Days 15 and 28 of Cycle 2. Efficacy assessments for patients with non-measurable ovarian or prostate cancer will be performed between Days 22 and 28 of all cycles. The assessment of cancer and the selection and reporting of radiological marker lesions or other assessment endpoints (CA-125 or PSA) are described in Section 5.6.

If efficacy evaluations on Day 28 of Cycle 2 demonstrate absence of disease progression, patients may be eligible to continue treatment with BAL101553.

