5.6 Efficacy assessments

At Screening, patients with advanced or recurrent solid tumors must have measurable disease (according to RECIST criteria v1.1), or non-measurable disease that can be followed by an acceptable tumor marker (CA-125 or PSA), prior to initiation of study treatment.

Patients with recurrent or progressive glioblastoma or high-grade glioma must be evaluated according to RANO criteria.

All radiological tests that demonstrated tumor at baseline (i.e., at Screening, or within 35 days prior to starting study drug for patients with advanced or recurrent solid tumors or within 15 days prior to starting study drug in patients with recurrent or progressive glioblastoma or high-grade glioma) must be repeated within 1 (Phase 1) or 2 (Phase 2a) weeks of completion of every even numbered cycle prior to the next administration of BAL101553. From Cycle 6 onwards, the interval between CT/MRI scans may be extended from 8 weeks to 12 weeks. Each lesion measured at baseline is to be measured throughout the study by the same method of assessment and the same technique (e.g., consistent use of CT with same anatomic coverage, contrast administration (unless medically contraindicated), slice thickness, and reconstruction interval at all time points) in order to allow for consistent assessments and comparisons. To determine complete response or partial response the required criteria must be present for at least 4 weeks.

Patients with objective response or stable disease will be permitted to continue to receive additional cycles of BAL101553 until disease progression or unacceptable toxicity. No patients are permitted to start subsequent cycles if unequivocal progression is observed, concerning mixed response see Section 4.4.

At study treatment completion (End of Study visit), radiology efficacy assessments must be repeated if these have not been performed within 35 days prior to this day. Assessment of CA-125 or PSA in patients with non-measurable ovarian or prostate cancer must be repeated if these have not been performed within 14 days prior to this day.

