5.6.3 Clinical progression

Patients who do not meet the criteria for progressive disease as described in Sections 5.6.1 and 5.6.2, but who exhibit signs and symptoms of clinical progression, will be considered for study purposes to have progressive disease.

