8.3.2.4 Dose-limiting toxicity, MAD determination and MTD recommendation

The dose-limiting toxicities will be listed by patient for each dose cohort.

The MAD is defined as the dose level at which DLT are observed during treatment Cycle 1 in \geq two of (up to) three patients with DLT in the first three patients of a dose cohort, or \geq two of (up to) six patients with DLT in a dose cohort that was expanded to six patients and at which dose escalation is being stopped.

The MTD is defined as the highest dose level below the MAD with an acceptable tolerability profile.

The MTD may be different for patients with advanced or recurrent solid tumors and for patients with recurrent or progressive GBM/high-grade glioma.

8.3.2.5 *Objective response rate*

The objective response rate will be calculated within the FAP (Phase 1 portion of the study), as the proportion of patients responding (i.e., with a best observed objective response of complete or partial response, based on RECIST criteria v1.1 for patients with advanced or recurrent solid tumors, CA-125 Rustin criteria for ovarian cancer, or PSA Working Group 2 criteria for prostate cancer); and based on RANO critieria for patients with recurrent or progressive GBM/high-grade glioma.

In the Phase 2a portion of the study (Simon's two-stage design), the patients with measurable disease at baseline in the EEP will be the primary population for the calculation of the objective response rate.

The proportion and its exact 95% confidence interval will be presented by dose cohort and by disease subgroup if appropriate.

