4.5 Pharmacokinetic analysis population(PK)

The PK analysis set includes all patients who received at least one dose of study drug and had at least one post-baseline PK assessment.

4.6 Efficacy-evaluable population (Phase 2a expansion portion of the study, Simon's two-stage design)

The efficacy evaluable population (EEP) is the subset of the FAP who had at least one post baseline RANO assessment after having received at least 6 weeks of study treatment.

For objective response rate and stage transition, the analysis will be based on patients with measurable disease at baseline in the EEP.

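### The Phase 2a response rate and both Simon decisions leave out and replace measurable-disease patients who fail before a qualifying RANO assessment, and no response rate in all dosed measurable-disease patients is planned beside them

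*Protocol*

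**What the plan says.** Protocol 8.3.1.5 defines the EEP as "the subset of the FAP who had at least one postbaseline RANO assessment after having received at least 6 weeks of study treatment". Membership therefore needs both the treatment duration and the assessment.

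For the primary endpoint, protocol 8.3.2.5 and SAP 6.2.1 say that "the patients with measurable disease at baseline in the EEP will be the primary population for the calculation of the objective response rate". SAP 4.6 extends this to the interim decision: "For objective response rate and stage transition, the analysis will be based on patients with measurable disease at baseline in the EEP". The interim trigger (protocol 8.3.2, SAP 3.4) uses the same condition, and the 2-of-9 and 6-of-19 rules (protocol 8.3.3.2, SAP 3.3.3) are worded for evaluable patients.

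On replacement, protocol 4.5 says that measurable-disease patients who discontinue "will be replaced if they did not have at least one postbaseline RANO assessment" following 6 weeks of treatment. Protocol 3.1.1 and SAP 3.3.1 agree: "patients with measurable disease at baseline will be replaced if they could not complete at least one post-baseline RANO assessment". None of these places makes an exception for progression, death or toxicity.

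Protocol 8.3.4 and SAP 5.2.1 count an unknown or unreported response as a non-response. For Phase 2a efficacy, the full analysis population (FAP) is named only for PFS and OS (protocol 8.3.2.7, SAP 6.2.3 and 6.2.4). SAP section 7 records no change from the protocol.

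**The concern.** Whether a patient enters the denominator depends partly on outcome. The protocol already treats several early exits as failures. Section 5.6.3 says that patients "who exhibit signs and symptoms of clinical progression, will be considered for study purposes to have progressive disease", and the RANO criteria in Appendix 6 include failure to return through death or deterioration as progression. A patient who stops in week 6 has a screening scan more than 35 days old, so section 5.3.3 requires an End of Study MRI. If that MRI shows progression, the patient has a PFS event in the FAP but is absent from the ORR and is replaced.

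The non-responder rule does not repair this, because it acts within a population that these patients never enter. The go/no-go count and the headline ORR therefore describe patients who stayed long enough to be assessed, and no planned estimate shows how far that differs from the rate in treated patients. With 9 and 19 patients, one or two losses move the estimate visibly.

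**Working it through.** **1. The plan's own figures.** Inputs from protocol 8.3.3.2: 9 patients in Stage 1, continue with 2 or more responses, 10 more patients, reject with 6 or more of 19; null rate 14%, alternative 40%.

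P(reject | p) = sum over x = 2 to 9 of P(Bin(9, p) = x) × P(Bin(10, p) ≥ 6 − x).

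At p = 0.14:
- x = 2: 0.2455 × 0.0400 = 0.0098
- x = 3: 0.0933 × 0.1545 = 0.0144
- x = 4: 0.0228 × 0.4184 = 0.0095
- x = 5: 0.0037 × 0.7787 = 0.0029
- x ≥ 6: 0.0004

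The total is 0.0371 (stated 3.7%). The same sum at p = 0.40 gives 0.8132 (stated 81%). Both are reproduced, and both refer to the response rate in evaluable patients.

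**2. Could an early leaver have been a responder?** Protocol 5.3.2.2: "Patients with measurable tumors will undergo radiological assessment of the tumor between Days 15 and 28 of Cycle 2". The first scheduled on-treatment scan is thus on day 28 + 15 = 43 at the earliest. Protocol 5.6: "To determine complete response or partial response the required criteria must be present for at least 4 weeks". On schedule, the earliest confirmed response is at about day 43 + 28 = 71. Progression or death before the qualifying scan is non-response under the protocol's own rules. For a patient who stops for toxicity, non-response is an imputation that this timing makes reasonable.

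**3. Effect on the reported rate at the cut-offs.** If k dosed measurable-disease patients are lost early without a response, the all-dosed ORR is responses / (evaluable + k). Intervals are exact (Clopper-Pearson). No assumption about the 14% is needed.

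| Decision | Early losses k | ORR | 95% CI |
|---|---|---|---|
| Final | 0 | 6/19 = 31.6% | 12.6–56.6% |
| Final | 2 | 6/21 = 28.6% | 11.3–52.2% |
| Final | 5 | 6/24 = 25.0% | 9.8–46.7% |
| Stage 1 | 0 | 2/9 = 22.2% | 2.8–60.0% |
| Stage 1 | 2 | 2/11 = 18.2% | 2.3–51.8% |

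**4. Conditional illustration for the error rate.** Suppose that 14% is an all-treated rate, that it is also the true treated rate, and that a share d of treated patients is excluded, all non-responders. The evaluable rate is then 0.14 / (1 − d). Putting it into the formula of step 1:
- d = 5%: rate 14.7%, rejection 4.6%
- d = 10%: rate 15.6%, rejection 5.8%
- d = 20%: rate 17.5%, rejection 9.3%

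Rejection exceeds 3.7% only if the treated rate is above 14% × (1 − d), that is 13.3%, 12.6% or 11.2%. With d = 20% and a treated rate of 8%, the evaluable rate is 0.08 / 0.80 = 10% and rejection is 0.8%.

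**5. The excluded share.** The documents do not give it for this cohort. Protocol 3.3 assumes about 25% non-evaluability: 54 + 40 × 1.25 = 104, so 10 of 50 (20%) of enrolled expansion patients. That figure covers all causes and includes non-measurable and surgical patients, so the values of d above are assumptions.

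**The case against.** The strongest reply is that the design is declared and consistent. Evaluable patients are named in the sample-size text, the replacement rule, the primary population and the interim trigger, and the operating characteristics are right for them. This stands: the request corrects no calculation and leaves the decision rule alone.

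Reporting is also better than the ORR text alone suggests. Protocol 8.3.4 lists reasons for discontinuation and provides summary tables, SAP 6.1.1 tabulates disposition for all enrolled patients, and SAP 6.1.3 summarises baseline data in both the FAP and the EEP. This stands for the final report. What is missing is a split by measurable disease, the reason for falling outside the EEP, and any such display at Stage 1.

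The effect may be small. Eligibility requires a life expectancy of at least 12 weeks and neurological stability (protocol 4.2), which should limit early losses without quantifying them, and the intervals in the table overlap widely.

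Two stronger readings are tempting. A reader might infer that the true type I error is well above 3.7%. The documents do not support this: protocol 1.5.2.2.1 does not state the denominator of the 14%, and 14% is the top of the cited 3–14% lomustine range. If it is an evaluable-patient rate, there is no inflation. A reader might also infer that no excluded patient could have responded. For toxicity leavers that goes too far: section 3.1.3 sets a minimum scan frequency, so earlier scans are possible, and SAP 5.1 takes response as reported on the case report form.

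**Conclusion.** The point holds as a cheap improvement. The Phase 2a ORR and both Simon decisions leave out and replace dosed measurable-disease patients who fail before the qualifying assessment, and no ORR that includes them is pre-specified. The reported ORR is then above the rate in treated patients whenever such losses occur and at least one response is seen. At the final cut-off the difference is 31.6 − 28.6 = 3.0 percentage points with two losses and 31.6 − 25.0 = 6.6 with five; at Stage 1 it is 22.2 − 18.2 = 4.0 with two.

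This rests on the early losses having no response: the protocol's own classification for progression and death, an imputation for toxicity. It concerns ORR only, since PFS and OS are also analysed in the FAP. The error-rate figures remain conditional illustrations and are not a finding that the stated 3.7% is wrong.

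**What to change.** Keep the EEP count as the governing rule, and say so, because the two rates may point in different directions near a cut-off.

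- **Supportive ORR.** In protocol 8.3.2 and 8.3.2.5 and SAP 3.4, 4.6 and 6.2.1, pre-specify an ORR with exact 95% CI in all dosed patients with measurable disease at baseline, shown beside the EEP ORR at the Stage 1 and final decisions. Replaced patients stay in the denominator. Those who progressed, died, stopped for toxicity or otherwise left before the qualifying RANO assessment without a response count as non-responders.
- **Stage 1 denominator.** The interim may be held early once enough responses are seen. Include only dosed measurable-disease patients who, by the data cut-off, either have the qualifying assessment or have discontinued. List those still on treatment and not yet assessed as pending, not as non-responders.
- **Disposition.** Extend the existing tables to give the number of dosed measurable-disease patients outside the EEP and the reason for each, at both decisions.
- **Operating characteristics.** In protocol 8.3.3.2 and SAP 3.3.3, state that 3.7% and 81% apply to evaluable patients.

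The cost is one extra table at each decision and a less favourable ORR beside the primary one. No extra patients are needed, and power under the governing rule is unchanged.
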